### **Brief Summary**

Older Veterans with PTSD have high rates of physical and psychological comorbidity and functional decline. This study tests whether a 6-month supervised, moderate-intensity exercise program improves PTSD symptoms and physical function compared with a Healthy Aging attention-control program.

### **Study Design**

- Study type: Interventional (clinical trial)
- Allocation: Randomized (1:1)
- Intervention model: Parallel assignment
- Masking: Outcomes assessor masked
- Primary purpose: Treatment / behavioral intervention
- Study duration per participant: 6 months

### **Arms and Interventions**

Experimental: Supervised Exercise (EX)

- 6-month, supervised, group-based exercise program delivered three times per week. Participants will have the option to participate virtually in group sessions (via video telehealth) or in the facility-based program.
- Multi-component program (aerobic, strength, balance, flexibility), progressing from light to moderate intensity using Borg RPE targets consistent with ACSM guidelines for older adults.

Control: Healthy Aging Attention Control (HA-ATC)

- 6-month program of up to 24 group workshops delivered via video and in person.

- Sessions cover aging-relevant topics (e.g., immunizations, medication management, nutrition, finances) and include brief gentle stretching; physical activity content is purposely minimized.

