### **Data Analysis and Statistical Considerations**

*General Considerations.* The basic design of the study is a two-arm parallel group, longitudinal intervention with replicate measures at baseline and 6 months. Randomization to the treatment groups will be stratified by gender. Since subjects are randomized to either EX or HA-ATC, and the groups should be equal at baseline, the analysis is straightforward. The primary and secondary analyses will be conducted on an intent-to-treat (ITT) basis; patients will be analyzed in the group to which they were randomized, regardless of intervention adherence. Additional supporting analyses focusing on alternative, more restrictive analytic cohorts (e.g., per protocol analysis) may be considered for exploratory analyses to provide additional information about the impact of exposure to the intervention. The main conclusions drawn from this trial will be based on the pre-specified primary and secondary hypotheses outlined below and will be tested with two-sided p-values at the standard 0.05 level. Results from exploratory analyses will be interpreted with appropriate consideration for their exploratory nature.

**Primary Analysis (Aim 1).** Our primary hypothesis ( $H_1$ ) is as follows: A 6-month structured exercise program will result in significantly greater improvements in PTSD symptoms (CAPS-5) and physical function (6MWT) when compared to HA-ATC.

**Secondary Analyses (Aim 2).** The secondary hypotheses of this study are:

The 6-month structured exercise program will result in significantly greater improvements in depression (PHQ-9) and sleep quality.

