The physical performance measures are all sub-maximal, self-paced tests that are age- and ability-appropriate for this patient population and are routinely used in clinical research. The physical performance tests include activities such as walking, standing, stepping, and stretching. These activities reflect common activities of daily living and as such, are associated with minimal risk for injury. However, there is a small risk of falls or muscle soreness with physical testing. To minimize risk of injury, these tests will be performed under supervision of trained research staff following standardized protocols.

The risk of doing moderate-intensity exercise is low, and may be associated with risk of injury, falls, fainting, dizziness, or muscle soreness. There is even the risk of sudden death or stroke. To minimize these risks during exercise, participants will be instructed to exercise at a comfortable level and to never push themselves to a point beyond where they feel safe. Participants will also be monitored and instructed to report symptoms such as unusual shortness of breath, dizziness, tightness or pain in the chest or arms, skipping heart beats, numbness, loss of balance, nausea, or blurred vision. In both conditions, there is a potential risk associated with the loss of confidentiality of study data. While it is

not possible to guarantee confidentiality in the group setting, all participants will be asked to sign a confidentiality agreement stating that disclosure of group member identities to anyone outside the group is not permissible.

We have also developed detailed SOPs in the case of serious adverse events during exercise testing or training (see attached). This includes:

- Calling 911 for emergencies (offsite exercise facility)
- Presence of a defibrillator on-site, and all research staff trained in use
- Glucose monitoring device and testing strips on-site, available as needed
- Daily monitoring of rating of perceived exertion (RPE) during exercise and patient reports of intensity

Risk of injury and adverse health events with exercise are further reduced by the presence of trained supervision (clinical exercise physiologist) at all times, with further support provided by the fitness facility staff trained in CPR and First Aid.

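### Both arms are treated in groups for 6 months, but the analysis section makes no provision for within-group correlation; if that correlation is positive, an independence analysis would exceed its 0.05 level

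*Combined protocol and SAP*

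**What the plan says.** Under Arms and Interventions, the exercise arm (EX) is a "6-month, supervised, group-based exercise program delivered three times per week". On format the section adds: "Participants will have the option to participate virtually in group sessions (via video telehealth) or in the facility-based program". The Healthy Aging control (HA-ATC) is a "6-month program of up to 24 group workshops delivered via video and in person". Both arms are therefore delivered in groups over the whole follow-up period.

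Study Design gives 1:1 randomisation, and Data Analysis and Statistical Considerations stratifies it by gender alone. Selection of Subjects gives a total of up to 188. The only statement on the form of the analysis is: "Since subjects are randomized to either EX or HA-ATC, and the groups should be equal at baseline, the analysis is straightforward". The primary and secondary hypotheses "will be tested with two-sided p-values at the standard 0.05 level", on an intention-to-treat basis. The section names no model and contains no term for class, workshop cohort or leader, no ICC, no design effect and no cluster-robust standard error.

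The Physical risks section describes a confidentiality agreement under which "disclosure of group member identities to anyone outside the group is not permissible". Group size, number of groups, and whether membership is fixed or rolling are not stated.

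**The concern.** Randomisation makes the arms comparable at the start. It does not make outcomes independent after 6 months of shared sessions, peers and supervision. If people in the same class tend to end up with similar CAPS-5 scores or walk distances because of the class, each participant carries less independent information than a simple two-sample comparison assumes. Standard errors are then too small, confidence intervals too narrow and p-values too low, for both primary outcomes and for the secondary ones. Intention-to-treat analysis does not address this.

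The reason the plan gives for a simple analysis, balance at baseline, does not bear on correlation that arises after randomisation. An analyst following the section as written would have no prompt to add a group term. If group membership is not recorded during the trial, it may be hard to reconstruct later, and a clustering adjustment chosen after the data are seen would be post hoc.

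**Working it through.** **Inputs from the document.** Two-sided level 0.05 (Data Analysis and Statistical Considerations); up to 188 randomised (Selection of Subjects) at 1:1 (Study Design), so 94 per arm; group delivery in both arms (Arms and Interventions).

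**Inputs assumed, because the document does not give them.** Group size m from 5 to 12; ICC from 0 to 0.10; equal-sized, non-overlapping groups with fixed membership.

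**Formulas.** Design effect DE = 1 + (m − 1) × ICC. True size of a nominal 0.05 z-test that ignores clustering = 2 × [1 − Φ(1.96/√DE)]. At DE = 1 this returns 0.050. That is only a consistency check, since 0.05 is a chosen level. The total of 188 cannot be reproduced, because the document gives no effect size, SD, power or dropout rate.

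**Clustering in both arms.** One case in full: m = 8, ICC = 0.05 gives DE = 1 + 7 × 0.05 = 1.35, √DE = 1.162, 1.96/1.162 = 1.687, size 0.092. The central cases are:

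| m | ICC | DE | True size | Effective N (188/DE) |
|---|---|---|---|---|
| any | 0 | 1.00 | 0.050 | 188 |
| 8 | 0.01 | 1.07 | 0.058 | 176 |
| 8 | 0.02 | 1.14 | 0.066 | 165 |
| 8 | 0.05 | 1.35 | 0.092 | 139 |
| 10 | 0.01 | 1.09 | 0.060 | 172 |
| 10 | 0.02 | 1.18 | 0.071 | 159 |
| 10 | 0.05 | 1.45 | 0.104 | 130 |

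Outside these cases, m = 5 with ICC 0.01 gives 0.055, and m = 12 with ICC 0.10 gives 0.176. The full assumed range is 0.050 to 0.176.

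**Clustering in one arm only.** The variance of the difference is inflated by (1 + DE)/2. For m = 8 and ICC 0.01 this is 1.035, size 0.054. For ICC 0.05 it is 1.175, size 0.071.

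**Simulation check.** A t-test with 94 per arm and clustering in both arms (40,000 runs per setting) rejected in 0.058, 0.066 and 0.090 of runs for m = 8 at ICC 0.01, 0.02 and 0.05. For m = 10 the figures were 0.061, 0.071 and 0.1005. These agree closely with the formula.

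**Cost of the correction.** From the design effect alone, intervals widen by √1.14 − 1 = 7% (m = 8, ICC 0.02) to √1.45 − 1 = 20% (m = 10, ICC 0.05). Small-sample degrees of freedom add to this. With m = 10 there are about 10 groups per arm, hence about 18 degrees of freedom. The critical value rises from 1.973 (186 df) to 2.101, a factor of 1.065, and 1.204 × 1.065 = 1.282, or about 28%.

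**The case against.** The strongest reply is that much of this is inference. The analysis section names no model, so it does not say that participants will be treated as independent. Its remark that "the groups should be equal at baseline, the analysis is straightforward" concerns balance between the two arms. This stands. A reader might infer that the plan commits to an independence analysis, but the document supports only that it permits one and makes no other provision.

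A reader might also infer that the 0.05 tests will in fact run at 0.06 to 0.10. The document does not support that, because it gives neither group size nor ICC. Any figure is conditional, and the range includes no inflation at all.

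The confidentiality agreement might be taken to show stable groups with known members. It shows only that there is a group setting. EX participants may choose video or facility sessions, and nothing says whether classes are closed or rolling. Fluid membership would weaken the correlation and make the first assigned group an approximation to exposure.

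The mechanism is also not certain. Exercise prescriptions are individualised. The document does not say that leaders differ between groups; one leader serving a whole arm would produce no between-group leader variance. Similarity that arises only because like people choose the same format does not inflate an individually randomised comparison; causal group influence does, and the formula does not separate the two. If assignment changed nobody's outcome, randomisation would protect the test size. The sizes above apply where group effects exist but average to no difference between arms.

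Finally, with only one or two running classes per arm, arm-specific group variances could barely be estimated. These points limit the claim and shape the remedy. They do not supply the missing provision.

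**Conclusion.** The point holds in conditional form. Both arms are group-delivered for 6 months, and the analysis section neither names a model nor provides for within-group correlation. If that correlation is positive and the analysis ignores it, the tests exceed their nominal level: about 0.058 to 0.104 with fixed groups of 8 to 10 in both arms and ICC 0.01 to 0.05, and about 0.054 to 0.071 if one arm clusters with 8 per group. At ICC zero the level is 0.05 as stated. The ICC may differ between CAPS-5 and the 6-minute walk, so the two primaries need not be affected equally. This is separate from any question of multiplicity across the two primaries.

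It is more than a missing detail, because a group term is unlikely to be added unprompted and depends on data that must be recorded. It should be fixed before analysis.

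**What to change.** 1. Record each participant's first assigned class or workshop group, including delivery mode, in both arms.
2. In Data Analysis and Statistical Considerations, name the primary model for CAPS-5 and the 6-minute walk test and define the group unit. Include a random effect for group within arm, with arm-specific variances where the number of groups allows, and Satterthwaite or Kenward-Roger degrees of freedom. Base the 0.05 tests on this model and use the same structure for the secondary outcomes.
3. Report the ICC for each outcome.
4. Pre-specify a fallback in case groups are too few or membership too fluid for a nested effect to be estimated: a simpler common-variance group effect, or a clustering sensitivity analysis.

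The cost is one data field and some SAP text. At ICC 0.02 to 0.05 with 8 to 10 per group, intervals widen by about 7 to 20% from the design effect, and by up to roughly 28% with the small-sample degrees of freedom. If the ICC is near zero, little changes. No clinical procedure is affected.

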### **Primary Outcome Measures**

- PTSD symptom severity (CAPS-5)
  - Measure: CAPS-5 total score
  - Time frame: Baseline, 6 months
  - Description: Clinician-Administered PTSD Scale for DSM-5 (CAPS-5) total score.
- Physical function (6-Minute Walk Test)
  - Measure: 6-minute walk test distance
  - Time frame: Baseline, 6 months
  - Description: Change in distance walked on the 6-minute walk test as an indicator of functional capacity.

### **Secondary Outcome Measures**

- Depressive symptoms (PHQ-9).
  - Time frame: Baseline, 6 months
- Sleep quality and disturbance (PSQI).
  - Time frame: Baseline, 6 months

### **Eligibility (abbreviated)**

#### Inclusion

- Veteran status
- Age ≥65 years.
- Reside within ~50-mile radius of Durham VAMC.
- Meet DSM-5 diagnostic criteria for PTSD as assessed with CAPS-5.

#### Key Exclusion

- Severe psychotic disorders or bipolar disorder in past 5 years.
- Prominent suicidal ideation or recent hospitalization for suicidality (past 6 months).
- Significant neurological disorders, uncontrolled diabetes, end-stage liver disease, dialysis, or conditions contraindicating moderate exercise.
- Physical disabilities that preclude safe use of exercise equipment (assistive devices allowed).

- Significant cognitive impairment or dementia.

### **Data Analysis and Statistical Considerations**

*General Considerations.* The basic design of the study is a two-arm parallel group, longitudinal intervention with replicate measures at baseline and 6 months. Randomization to the treatment groups will be stratified by gender. Since subjects are randomized to either EX or HA-ATC, and the groups should be equal at baseline, the analysis is straightforward. The primary and secondary analyses will be conducted on an intent-to-treat (ITT) basis; patients will be analyzed in the group to which they were randomized, regardless of intervention adherence. Additional supporting analyses focusing on alternative, more restrictive analytic cohorts (e.g., per protocol analysis) may be considered for exploratory analyses to provide additional information about the impact of exposure to the intervention. The main conclusions drawn from this trial will be based on the pre-specified primary and secondary hypotheses outlined below and will be tested with two-sided p-values at the standard 0.05 level. Results from exploratory analyses will be interpreted with appropriate consideration for their exploratory nature.

**Primary Analysis (Aim 1).** Our primary hypothesis ( $H_1$ ) is as follows: A 6-month structured exercise program will result in significantly greater improvements in PTSD symptoms (CAPS-5) and physical function (6MWT) when compared to HA-ATC.

**Secondary Analyses (Aim 2).** The secondary hypotheses of this study are:

The 6-month structured exercise program will result in significantly greater improvements in depression (PHQ-9) and sleep quality.

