### **Selection of Subjects**

The proposed study will randomize up to 188 patients. Because there may be differences in responses to the intervention by gender, we will stratify randomization by gender. Participants will be Veterans 1) aged 65 years or older; 2) live within a 50 mile radius of DVAMC; and 3) meet diagnostic criteria for PTSD (CAPS-5).

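### The analysis section relies on expected baseline equality and specifies no adjustment for baseline values or gender; one pre-specified ANCOVA for all four outcomes would gain precision without new data

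*Combined protocol and SAP*

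**What the plan says.** The only statistical section of the combined protocol and SAP is Data Analysis and Statistical Considerations. It describes a two-arm design, "longitudinal intervention with replicate measures at baseline and 6 months", with randomisation stratified by gender. On method it says: "Since subjects are randomized to either EX or HA-ATC, and the groups should be equal at baseline, the analysis is straightforward". It adds an intent-to-treat rule and states that the hypotheses "will be tested with two-sided p-values at the standard 0.05 level". No model, test or covariate is named for any outcome, and no analysis is said to include gender.

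Under Primary Outcome Measures, CAPS-5 is given as "Measure: CAPS-5 total score" and 6MWT as "Change in distance walked on the 6-minute walk test as an indicator of functional capacity". Both have baseline and 6 months as their time frame, as do PHQ-9 and PSQI under Secondary Outcome Measures. The primary hypothesis is framed as larger improvement on both CAPS-5 and 6MWT. On size, Selection of Subjects says: "The proposed study will randomize up to 188 patients"; Study Design gives 1:1 allocation.

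**The concern.** Expected equality at baseline is offered as the reason the analysis is simple. Randomisation does not make the arms equal in the trial actually run, and gender is the only factor balanced by design. Baseline CAPS-5 and 6MWT are left to chance.

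Three analyses fit the text: comparing 6-month values, comparing changes, or comparing 6-month values adjusted for baseline. All are valid on average, but they differ in precision and give different estimates whenever the baseline means differ. The two primaries are also described in different terms, with no model to bring them together. Precision on all four outcomes is at stake, and so is a choice of primary estimate that could still be made after the data are seen.

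**Working it through.** **Inputs from the documents.** Up to 188 randomised 1:1, so 188/2 = 94 per arm; two-sided alpha 0.05; one baseline and one 6-month measurement. The documents state no power, effect size, SD, correlation or dropout, so there is no figure of the plan's own to reproduce.

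**Assumptions.** Correlation r between baseline and 6 months of 0.5 to 0.7, with 0.3 and 0.85 as outer cases; equal variances at the two times; 80% power; all 94 per arm measured at 6 months; normal approximation. Results are in SD units of the outcome.

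**Step 1: chance imbalance.** SE of the baseline difference = sqrt(2/94) = 0.146 SD. The 95% range is ±1.96 × 0.146 = ±0.286 SD.

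**Step 2: conditional error.** Given a baseline difference D, the 6-month comparison is off by rD and the change comparison by (r − 1)D. At D = 0.286 SD:
- r = 0.5: +0.14 SD and −0.14 SD.
- r = 0.7: +0.20 SD and −0.09 SD.

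The two estimates always differ by rD − (r − 1)D = D. ANCOVA removes both errors under the linear model.

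**Step 3: relative variance of the arm difference.** 6-month value: 1. Change: 2(1 − r). ANCOVA: 1 − r². The ANCOVA saving is therefore r² against the 6-month value and (1 − r)/2 against change.

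| Assumed r | Change | ANCOVA | Saving vs 6-month value | Saving vs change |
|---|---|---|---|---|
| 0.3 | 1.40 | 0.91 | 9% | 35% |
| 0.5 | 1.00 | 0.75 | 25% | 25% |
| 0.6 | 0.80 | 0.64 | 36% | 20% |
| 0.7 | 0.60 | 0.51 | 49% | 15% |
| 0.85 | 0.30 | 0.2775 | 72% | 7.5% |

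**Step 4: detectable effect at 80% power.** (1.960 + 0.842) × sqrt(2/94) × sqrt(relative variance) = 0.409 × sqrt(relative variance).
- 6-month value: 0.409 SD at any r.
- r = 0.6: change 0.409 × sqrt(0.80) = 0.366; ANCOVA 0.409 × sqrt(0.64) = 0.327.
- r = 0.85: change 0.224; ANCOVA 0.215.

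**Step 5: the same in power, for a true effect of 0.409 SD.** In the order 6-month value, change, ANCOVA: 80%, 80% and 90% at r = 0.5; 80%, 95% and 97.5% at r = 0.7.

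**The case against.** The plan is silent on adjustment; it does not reject it. A reader might infer that an unadjusted analysis has been chosen, but the text does not support that. The design is called longitudinal, the hypothesis concerns improvement (which implies some use of baseline), and equal expected baselines are exactly the premise of a longitudinal model with a common baseline mean. That model would use baseline much as ANCOVA does. This part of the objection stands: the defect is an unspecified model resting on a weak justification.

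The 6-month-only comparator is also just one reading. The CAPS-5 entry names the instrument's score at two time points and does not say that the 6-month score is analysed alone. The larger savings in the table apply only on that reading. For 6MWT, described as change, the relevant saving is (1 − r)/2, which cannot reach 50% for any r above zero. If r were 0.85, the gain would be about 0.01 SD in detectable effect.

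Finally, chance imbalance is ordinary sampling variation and is already reflected in the standard error. It neither biases the randomised comparison on average nor inflates type I error. This too stands.

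None of it removes the case for acting. If the wording fits several models that give different estimates, the primary analysis is left to inference, and under the working assumptions ANCOVA is at least as precise as either alternative at every r.

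**Conclusion.** The point holds as a gap in specification with a measurable cost in precision. No adjustment for baseline or gender is specified, and expected equality is not a reason to leave it out. Assuming r of 0.5 to 0.7, ANCOVA saves 15–25% of the variance against change scores and, if CAPS-5 is to be analysed as the 6-month value alone, 25–49% against that. At r = 0.85 the saving against change is 7.5%. These figures rest on an r that the documents do not give, on equal variances and on complete follow-up of 188, so no single percentage should be quoted as the plan's loss. No gain is claimed for gender, where the expected 8% female share is about 15 of 188; it belongs in the model because randomisation is stratified on it.

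A reader might also infer that a constrained longitudinal model would recover information from participants without a 6-month value. It would not. With one post-baseline visit the likelihood splits into a baseline part and a part for the 6-month value given baseline. The arm effect appears only in the second, so baseline-only participants add essentially nothing, and the result matches complete-case ANCOVA. The lack of a missing-data rule is a separate matter that this change does not settle.

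**What to change.** Delete the sentence that infers simplicity from equal baselines. In its place pre-specify one model for CAPS-5, 6MWT, PHQ-9 and PSQI: ANCOVA of the 6-month value on arm, the baseline value of that outcome and gender, or the equivalent constrained longitudinal model. State that the adjusted arm difference at 6 months, with its 95% confidence interval, is the effect measure for both primaries, and align the CAPS-5 and 6MWT outcome descriptions with it. With baseline in the model, the arm coefficient is the same whether the outcome is entered as the 6-month value or as the change, so the improvement hypotheses can stay as worded. If an expected gain is quoted, show it over a range of r and label r as an assumption.

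The cost is one paragraph of SAP wording. No new data are needed: baseline values of all four outcomes are already scheduled, and gender is recorded for stratification.
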